Appendix 2 Adverse Event and Prior/Concomitant Medication Date Imputations

Adverse Event Start/Stop Date Imputation

Imputatio	on Rules for	Partial Dates (D = day, M = month, Y =	year)

Parameter	Missing	Additional Conditions	Imputation
Start date	D	M and Y same as M and Y of first dose of study drug	Date of first dose of study drug
for AEs	D	M and/or Y not same as date of first dose of study drug	First day of month
		Y same as Y of first dose of study drug	Date of first dose of study drug
	D and M	Y prior to Y of first dose of study drug but same as Y of screening date	Date of screening date
	D, M, Y	None - date completely missing	Date of first dose of study drug
Stop date	D	M and Y same as M and Y of last dose of study drug	Date of last dose of study drug
for AEs	D	M and/or Y not same as date of last dose of study drug	Use last day of month
	D and M	Y same as Y of last dose of study drug	Date of last dose of study drug
	D and W	Y not same as Y of last dose of study drug	Use Dec 31
	D, M, Y	None - date completely missing	No imputation, but assume ongoing

Note: In all cases, if an estimated start date is after a complete stop date, use the first day of the stop date month. Similarly, if the estimated stop date is before a complete or imputed start date, use the last day of the start day month. In all cases, if it cannot be determined if the adverse event occurred prior to or after the first dose of test article, the adverse event should be defined as treatment emergent.

Prior and Concomitant Medication Start Date Imputation

Parameter	Type of Medication	Imputation
Start date for con meds	Non- Antibacterial	If it cannot be determined whether or not the start date of a medication (non-antibacterial) is prior to the first dose of study drug, it will be assumed that the medication was received prior to the first dose of study drug.
	Antibacterial	Missing start dates for antibacterials will be queried for a value. If it cannot be determined whether or not the start date of an antibacterial is prior to the first dose of study drug, it will be assumed that the medication was received prior to the first dose of study drug unless the indication notes that the medication was received after the first dose of study drug.
Stop date for con meds	Non- Antibacterial	If it cannot be determined whether or not the stop date of a medication (nonantibacterial) is after the first dose of study drug, it will be assumed that the medication was received after the first dose of study drug
	Antibacterial	Missing stop dates for antibacterials will be queried for a value. If it cannot be determined whether or not the stop date of an antibacterial is after the first dose of study drug, it will be assumed that the medication was received after the first dose of study drug unless the indication notes that the medication was received prior to the first dose of study drug. If it cannot be determined whether the antibacterial was received prior to the assessment of Early Clinical Response, the EOT and/or the PTE Visit, the antibacterial will be assumed to have been received through the PTE Visit.

Appendix 3 Modified Division of Microbiology and Infectious Diseases Adult Toxicity Table

The DMID Adult Toxicity Table (21-NOV-2007) was modified to exclude the clinical component of the toxicity grading because clinical signs and symptoms related to abnormal laboratory values are not collected in this study. In addition, Grade 0 was added to the table so that shifts from normal could be analyzed. Grades for enzymes were modified as indicated in the table below.

For toxicity grades based on a multiple of the ULN, the normal range from the central laboratory will be applied.

For toxicity grades based on fixed values, the grades will be assigned regardless of the normal actual range values from the central laboratory. For example, a hemoglobin value of 10.0 gm/dL will be assigned a grade of 1 toxicity, even if the lower limit of normal from the laboratory was 9.8 gm/dL.

HEMATOLOGY									
	Grade 0	Grade 1	Grade 2	Grade 3	Grade 4				
Hemoglobin (gm/dL)	> 10.5	9.5-10.5	8.0-9.4	6.5-7.9	< 6.5				
Absolute Neutrophil Count (count/mm ³)	> 1500	1000-1500	750-999	500-749	< 500				
Platelets (count/mm ³)	\geq 100,000	75,000-99,999	50,000-74,999	20,000-49,999	< 20,000				
WBCs (count/mm ³)	1000-10,999	11,000-12,999	13,000-14,999	15,000-30,000	> 30,000 or < 1,000				

		CHEMISTRY	Y		
	Grade 0	Grade 1	Grade 2	Grade 3	Grade 4
Hyponatremia (mEq/L)	> 135	130-135	123-129	116-122	< 116
Hypernatremia (mEq/L)	< 146	146-150	151-157	158-165	> 165
Hypokalemia (mEq/L)	> 3.4	3.0-3.4	2.5-2.9	2.0-2.4	< 2.0
Hyperkalemia (mEq/L)	< 5.6	5.6-6.0	6.1-6.5	6.6-7.0	> 7.0
Hypoglycemia (mg/dL)	≥ 65	55-64	40-54	30-39	< 30
Hyperglycemia (mg/dL) (nonfasting and regardless of prior history of diabetes)*	< 116	116-160	161-250	251-500	> 500
Hypocalcemia (mg/dL) (corrected for albumin)	> 8.4	8.4-7.8	7.7-7.0	6.9-6.1	< 6.1
Hypercalcemia (mg/dL) (correct for albumin)	≤ 10.5	10.6-11.5	11.6-12.5	12.6-13.5	> 13.5
Hypomagnesemia (mEq/L)	> 1.4	1.4-1.2	1.1-0.9	0.8-0.6	< 0.6
Hypophosphatemia (mg/dL)	≥ 2.5	2.0-2.4	1.5-1.9	1.0-1.4	< 1.0
Hyperbilirubinemia (total bilirubin)	< 1.1×ULN	1.1-1.5×ULN	> 1.5- 2.5×ULN	> 2.5-5×ULN	> 5×ULN
Urea	< 1.25×ULN	1.25-2.5×ULN	> 2.5-5×ULN	> 5-10×ULN	$> 10 \times ULN$
Hyperuricemia (uric acid) (mg/dL)	< 7.5	7.5–10.0	10.1–12.0	12.1–15.0	> 15.0
Creatinine	< 1.1×ULN	1.1-1.5×ULN	> 1.5- 3.0×ULN	> 3.0-6×ULN	>6×ULN

*The DMID toxicity table reports hyperglycemia detected in nonfasting specimens obtained from subjects with no prior diabetes.

ENZYMES										
	Grade 0	Grade 1	Grade 2	Grade 3	Grade 4					
AST (SGOT)	< 1.25×ULN	1.25-2.5×ULN	> 2.5-5×ULN	> 5-10×ULN	>10×ULN					
ALT (SGPT)	< 1.25×ULN	1.25-2.5×ULN	> 2.5-5×ULN	> 5-10×ULN	>10×ULN					
GGT	< 1.25×ULN	1.25-2.5×ULN	> 2.5-5×ULN	> 5-10×ULN	>10×ULN					
Alkaline	< 1.25×ULN	1.25-2.5×ULN	> 2.5-5×ULN	> 5-10×ULN	>10×ULN					
Phosphatase										
Amylase	< 1.1×ULN	1.1-1.5×ULN	> 1.5-2.0×ULN	> 2.0-5.0×ULN	> 5.0×ULN					
Lipase	< 1.1×ULN	1.1-1.5×ULN	> 1.5-2.0×ULN	> 2.0-5.0×ULN	> 5.0×ULN					

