6.2 Inclusion and Exclusion Criteria

Each subject must meet all of the following criteria to be enrolled in this study:

Main Criteria for Inclusion:

- 1. Written and signed informed consent must be obtained before any protocol specific assessment is performed.
- 2. Male or female, age 18 years or older.
- 3. Has at least 3 of the following symptoms:
 - Cough
 - Production of purulent sputum
 - Dyspnea (shortness of breath)
 - Pleuritic chest pain
- 4. Has at least TWO of the following abnormal vital signs:
 - Fever or hypothermia documented by the investigator (temperature > 38.0°C [100.4°F] or < 36.0°C [95.5°F])
 - Hypotension with systolic blood pressure (SBP) < 90 mm Hg
 - Heart rate > 90 beats per minute (bpm)
 - Respiratory rate (RR) > 20 breaths/minute
- 5. Has at least 1 clinical sign or laboratory finding associated with CABP:
 - Hypoxemia (partial pressure of arterial oxygen [PaO₂] < 60 mm Hg by arterial blood gas [ABG] or oxygen saturation < 90% by pulse oximetry)
 - Physical examination findings of pulmonary consolidation (eg, dullness on percussion, bronchial breath sounds, or egophony)
 - An elevated total white blood cell (WBC) count (> 12,000 cells/mm³) or leucopenia (WBC < 4,000 cells/mm³) or elevated immature neutrophils (> 15% band forms), see % bands calculation in Appendix 2 (regardless of total peripheral WBC count)
- 6. Has disease categorized as being PORT Risk Class II or III at Screening where initiation of antibiotics with oral therapy is appropriate in the opinion of the investigator, whether inpatient or outpatient setting (see PORT Risk Class calculation in Appendix 4).

- 7. Radiographically-confirmed pneumonia, ie, new or progressive pulmonary infiltrate(s) on chest X-ray (CXR) or chest computed tomography (CT) scan consistent with acute bacterial pneumonia within 48 hours prior to the first dose of test article.
- 8. Ability to swallow up to 3 tablets in succession.
- 9. Females must have a negative urine pregnancy test at Screening and agree to comply with using an acceptable method of birth control as per your local requirements (eg, abstinence, oral contraceptive, intrauterine device [IUD], barrier contraception [condom], tubal ligation, hysterectomy, bilateral oophorectomy, postmenopausal, or vasectomized partner) from Screening through PTE. Males must agree to use an acceptable method of birth control with female partner(s) and must not donate sperm from Screening through PTE.

Main Criteria for Exclusion:

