6.2 Demographics and Baseline Characteristics

Except where indicated, demographic data and baseline characteristics will be presented for the ITT population. A table will present the subject demographics (e.g., gender, age, ethnicity, and race) and baseline characteristics (height, weight, BMI, and creatinine clearance categorized before the start of test article as:

- severe renal impairment [< 30 mL/min],
- moderate renal impairment [30-50 mL/min],
- mild renal impairment [> 50-80 mL/min], and
- normal renal function [> 80 mL/min]).

Age will be calculated from the date of birth to the informed consent date. Age will be summarized as a continuous variable and in the categories, 18-45, >45-65, and >65 years.

Creatinine clearance will be calculated from the local laboratory data since these data were used for determination of the inclusion and exclusion criteria and will be determined from the Cockcroft-Gault equation.

A table will provide the frequency counts and percentages for subjects who received prior antibiotics, and PORT Risk Class (from the eCRF) for the ITT population. PORT score will also be summarized as a continuous variable.

Baseline assessments of clinical symptoms, clinical signs, abnormal vital signs, and abnormal laboratory signs of CABP will be presented for the ITT, and PK populations.

The number and percentage of subjects with each of the CABP symptoms (cough, pleuritic chest pain, dyspnea, and phlegm/sputum production) by severity (absent, mild, moderate, severe) will be presented. The number and percentage of subjects with the presence by severity (i.e., absent, mild, moderate, severe) of the following clinical signs will be provided: rales, rhonchi, dullness on percussion, bronchial breath sounds, wheezing, decreased breath sounds, and egophony. The number and percentage of subjects with fever (defined as body temperature > 38°C [100.4°F] oral or rectal), hypothermia (defined as body temperature < 36°C [95.5°F] oral or rectal), hypotension with systolic blood pressure < 90 mmHg, heart rate > 90 bpm, respiratory rate > 20 breaths/min, hypoxemia (defined as PaO₂ < 60 mmHg by arterial blood gas or oxygen saturation < 90% by pulse oximetry), elevated total WBC count (> 12,000 cells/mm³), leucopenia (WBC < 4,000 cells/mm³), elevated immature neutrophils (> 15% band forms regardless of total peripheral WBC count) and any of elevated total WBC count, leucopenia or elevated immature neutrophils will be summarized.

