8.3 Laboratory Values

Summaries of laboratory data will include hematology, and chemistry, parameters. Laboratory parameters will be presented in alphabetic order with the following exceptions: differentials of white blood cell (WBC) counts will be presented following the WBC results, and chemistry parameters will first be grouped by organ class (renal, liver, electrolytes, and other) and presented alphabetically within each of these classes, as shown below.

Organ Class	Laboratory Parameter
Renal	Creatinine
Renal	Urea
Liver	Alkaline phosphatase (ALP)
Liver	ALT
Liver	AST
Liver	Total Bilirubin
Liver	GGT
Electrolytes	Bicarbonate
Electrolytes	Calcium
Electrolytes	Chloride
Electrolytes	Magnesium
Electrolytes	Potassium
Electrolytes	Sodium
Other	Albumin
Other	Amylase
Other	Blood glucose
Other	Cholesterol
Other	CK
Other	LDH

Table 1.Laboratory Parameters and Organ Class

Organ Class	Laboratory Parameter
Other	Lipase
Other	Phosphate
Other	Total protein
Other	Uric acid

Table 1.Laboratory Parameters and Organ Class

Baseline is defined the local lab value that is closest to and prior to the first dose of study drug.

Several analyses of the laboratory data will be presented. Descriptive statistics (based on International System [SI] units) for chemistry, hematology and the change from baseline will be summarized by treatment group at each time point (EOT Visit and PTE Visit), and for the overall worst value post-baseline (which includes unscheduled visits).

Clinically notable laboratory values will be defined as any lab values with at least a 2-grade increase from baseline. Shift tables will be presented to show the number of subjects with a laboratory value with a grade of 0, 1, 2, 3 or 4 at baseline versus the value at each visit and the worst post-baseline value. Number and percentage of subjects with at least a 2-grade increase from baseline (based on DMID criteria shown in Appendix 3) will be summarized. Percentages for each laboratory test will be based on the number of subjects with a baseline and post-baseline evaluation of the specific laboratory test. A listing will be provided which gives all laboratory results for a given laboratory test for subjects who have at least one 2-grade increase from baseline.

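### On the SAP's WBC toxicity row, counts of 1,000 to 3,999 cells/mm³ are Grade 0 although the trial calls them leucopenia, so the WBC shift table and notable flag miss them

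*SAP*

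**What the plan says.** SAP Appendix 3 modifies a published toxicity table and gives the reason for its extra category: "In addition, Grade 0 was added to the table so that shifts from normal could be analyzed". The WBC row (cells/mm³) reads: Grade 0, 1,000 to 10,999; Grade 1, 11,000 to 12,999; Grade 2, 13,000 to 14,999; Grade 3, 15,000 to 30,000; Grade 4, "> 30,000 or < 1,000". For tests graded on fixed values, "the grades will be assigned regardless of the normal actual range values from the central laboratory".

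SAP 8.3 builds two outputs on these grades. The first is the flag: "Clinically notable laboratory values will be defined as any lab values with at least a 2-grade increase from baseline". The second is the shift analysis: "Shift tables will be presented to show the number of subjects with a laboratory value with a grade of 0" to 4 at baseline against each visit and against the worst post-baseline value. SAP 2.1 lists clinically notable laboratory parameters under the secondary (safety) endpoint.

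Elsewhere the lower limit for WBC is 4,000. Inclusion criterion 5 in Protocol 6.2 accepts "leucopenia (WBC < 4,000" cells/mm³ as a finding associated with CABP. SAP 6.2 summarizes "leucopenia (WBC < 4,000 cells/mm³" as an abnormal baseline sign. SAP 9.3 uses 4,000 as the low bound for WBC stabilization.

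**The concern.** The stated purpose of Grade 0 is to represent normal, so that movement away from normal can be counted. On the WBC row it also takes in counts that the same documents call abnormal. A subject whose WBC falls into that range on treatment is recorded in the shift table as staying in, or moving to, Grade 0, and the WBC flag stays silent.

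The case that could mislead is a raised baseline. Inclusion criterion 5 lists "An elevated total white blood cell (WBC) count (> 12,000 cells/mm³" among its qualifying findings, so some subjects may enter at Grade 1 or higher. If such a subject then becomes leucopenic, the table entry is the same as for a subject whose count has returned to normal.

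At stake is the accuracy of one row of a safety shift table and of one automatic flag. The PK endpoint is not affected.

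**Working it through.** **Step 1. Is the row consistent with itself?** Grade 0 starts at 1,000, where the low part of Grade 4 (below 1,000) ends. It stops at 10,999, just before Grade 1 starts at 11,000. The limits meet at both ends, so the 1,000 is not a text-extraction error.

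**Step 2. Compare with the trial's own limit.** Leucopenia is WBC below 4,000 and Grade 0 is 1,000 to 10,999. The overlap is 1,000 to 3,999.

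**Step 3. Apply the SAP 8.3 rule.** A value is notable if (post-baseline grade − baseline grade) is at least 2.

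- Post-baseline 1,000 to 3,999: the change is 0 − baseline grade, which is never above 0. The WBC flag cannot fire from any baseline.
- Post-baseline below 1,000: the change is 4 − baseline grade. This is at least 2 only if the baseline grade is 2 or lower, that is, a baseline of 1,000 to 14,999. From 15,000 to 30,000 it is 4 − 3 = 1. From above 30,000 it is 4 − 4 = 0.

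| Baseline WBC | Post-baseline WBC | Grades | Change | Notable on WBC row |
|---|---|---|---|---|
| 8,000 | 1,000 | 0 to 0 | 0 | no |
| 12,500 | 1,500 | 1 to 0 | −1 | no |
| 14,000 | 3,000 | 2 to 0 | −2 | no |
| 16,000 | 2,000 | 3 to 0 | −3 | no |
| 8,000 | 999 | 0 to 4 | +4 | yes |
| 16,000 | 999 | 3 to 4 | +1 | no |
| 31,000 | 999 | 4 to 4 | 0 | no |

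**Step 4. How much does the neutrophil row recover?** Appendix 3 grades the absolute neutrophil count (ANC) as Grade 0 above 1,500, Grade 1 at 1,000 to 1,500, Grade 2 at 750 to 999, and higher grades below that. Let p be the neutrophil share of WBC, so ANC = p × WBC. The documents give no value for p. I assume 60%, with a range of 40% to 80%. From a baseline ANC of Grade 0, a 2-grade rise needs ANC below 1,000, that is, WBC below 1,000/p.

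| Assumed p | ANC still Grade 0 when WBC is above 1,500/p | ANC notable when WBC is below 1,000/p | WBC range flagged by neither row |
|---|---|---|---|
| 40% | 3,750 | 2,500 | 2,500 to 3,999 |
| 60% | 2,500 | about 1,667 | about 1,667 to 3,999 |
| 80% | 1,875 | 1,250 | 1,250 to 3,999 |

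At 60%, a fall to a WBC of 1,500 gives ANC = 0.60 × 1,500 = 900, which is Grade 2, so the neutrophil row flags it. It would escape only if p were at least 1,000/1,500, about 67%. A fall to 3,000 gives ANC = 0.60 × 3,000 = 1,800, which is Grade 0, and neither row flags it.

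**The case against.** The strongest reply is that low counts are visible elsewhere. SAP 8.3 gives descriptive statistics for hematology and change from baseline at EOT, at PTE and for the worst post-baseline value. Subject listings flag values outside normal limits as low or high. Protocol 8.18.4 has clinically significant laboratory abnormalities recorded as AEs. With up to 30 subjects in a single arm, and no formal comparisons under Protocol 12.8, a reader of the listings could see every low value. Hemoglobin and platelets have their own low-side grades, and the neutrophil row catches many of the deeper falls. All of this stands, and it keeps the point minor. It does not correct the shift table or the notable count.

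A second reply is that 4,000 is used in the protocol as a diagnostic sign of CABP and not as a toxicity threshold, and that Appendix 3 states no change to WBC Grades 1 to 4. On that view Grade 0 is only what those grades leave uncovered. That explains how the range arose. But Grade 0 is the SAP's own addition, made to stand for normal, and the 4,000 limit is the only lower bound for WBC that the trial uses elsewhere. The table also already gives sodium, potassium, glucose and calcium separate low and high rows. The content of the published scale cannot be checked from these documents, and nothing here depends on it.

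A reader might infer that the laboratory safety analysis as a whole cannot detect a fall in WBC until it is below 1,000. The documents do not support that: it ignores the neutrophil row, the descriptive summaries and the listing flags. A reader might also infer that raised WBC is common at entry. Inclusion criterion 5 needs only one of three kinds of finding, and no frequency is given, so raised WBC is possible at entry and no more can be said.

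**Conclusion.** The point holds, within limits. On the WBC row, a post-baseline count of 1,000 to 3,999 can never be clinically notable, and from a raised baseline it tabulates as a shift to Grade 0. Because high and low extremes share Grade 4, a fall below 1,000 from a baseline of 15,000 or more is not notable on that row either. These results follow from the table and the 2-grade rule with no further assumption.

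The size of the gap after allowing for neutrophil grading does rest on an assumption. At 60% neutrophils and a baseline ANC of Grade 0, falls to a WBC of about 1,667 to 3,999 are flagged by neither row. The lower end of that range moves between 1,250 and 2,500 as the assumed share runs from 80% to 40%. How many subjects would fall there cannot be estimated from the documents.

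The consequence is confined to the WBC shift table and the WBC notable flag in a descriptive safety analysis. The change is worth making because it is cheap, but no main conclusion of the trial depends on it.

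**What to change.** In SAP Appendix 3 and 8.3:

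- Report low WBC separately from high WBC in the shift table, as the table already does for sodium, potassium, glucose and calcium. The two parts of Grade 4 (above 30,000 and below 1,000) then no longer share a cell.
- Flag and count as clinically notable any post-baseline WBC below 4,000 when baseline was 4,000 or more. This uses the trial's own limit and also covers falls below 1,000 from a baseline of 15,000 or more.
- Keep below 1,000 as Grade 4 on the low side, so that a subject who enters at 1,000 to 3,999 and falls below 1,000 is still flagged, as now.

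Any finer low-side grades are for the sponsor to set, because the documents give no cut-points for them.

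The cost is one SAP table edit, one extra output row and a few more flagged values. No new data are needed, since hematology is already collected at Screening, EOT and PTE.

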Appendix 4 Criteria for Clinically Notable Vital Signs

Vital Sign Parameter	Flag	Criterion Value	Change from Baseline
Systolic Blood Pressure (mmHg)	High (CH)	≥ 180	Increase of $\geq 20 \text{ mmHg}$
	Low (CL)	≤ 90	Decrease of $\geq 20 \text{ mmHg}$
Diastolic Blood Pressure (mmHg)	High (CH)	≥ 105	Increase of $\geq 15 \text{ mmHg}$
	Low (CL)	≤ 50	Decrease of $\geq 15 \text{ mmHg}$
Heart Rate (bpm)	High (CH)	≥ 120	Increase of ≥ 15 bpm
	Low (CL)	≤ 50	Decrease of ≥ 15 bpm
